3.3. Substantiation of the study construction

This is a non-interventional Observational Study focusing on the assessment of the efficacy of the treatment with the **HEDUSSIN**® medicinal product. No additional diagnostic or monitoring procedures will be applied and the analysis of the gathered data will be performed using epidemiological methods only.

The Study aims to gather data on the efficacy of the treatment with the **HEDUSSIN®** medicinal product [the duration of the infection, the symptoms associated with the respiratory system] and the evaluation of the overall wellbeing of the Patient as well as the tolerance of the treatment in the Patient population where the **HEDUSSIN®** medicinal product will be used as part of the routine therapy and in accordance with the terms of the marketing authorization and in the manner specified in the Summary of Product Characteristics. Collection of such data in the population of Polish patients is very important from the scientific and practical point of view as **HEDUSSIN®**, a medicinal product containing dry extract of common ivy leaves in the form of syrup, obtained the marketing authorisation for medicinal products in 2015. The

data will be used for the purposes of planned marketing campaigns as well as staff and doctor training.

The study is scheduled for 3 months and will be conducted in 500 patients diagnosed with productive (wet) cough of various aetiologies who started the treatment with the **HEDUSSIN**® medicinal product as part of the routine therapy. The observation of the efficacy in a single patient will continue up to 10 days. During this time, centres will collect data on the efficacy of the treatment which will be recorded in the Study Questionnaire. The Study Questionnaires will also be recording data on the tolerability of the treatment. The Study Questionnaires will then be returned to the ordering party in order to develop the report.

3.4. Duration of the Study

The Observation of the Patients during the Study will continue up to 10 days from the date of the first visit. The number of assessments will not influence neither the number of visits nor the amendment of the therapy application as specified in the SPCh criteria. The duration of the study is 3 months.

4. COMPLIANCE WITH TERMS OF GOOD CLINICAL PRACTICE, ETHICAL ISSUES

This is a non-interventional study and thus is not subject to the provisions of the 2001/20/WE Clinical Trial Directive of the European Parliament and of the Council of Europe of 4 April 2001.

The study will be conducted in accordance with all applicable provisions of the local law.

5. STUDY POPULATION

5.1. Records of the Study participants

Each Investigator will be required to keep a list of patients included in the study. The list should include the Patient number, their name and surname, initials and date of birth, and must be kept confidentially at the study centre.

The study is planned to include 500 patients treated in Poland by 50 paediatricians, general practitioners, internists, allergists and pulmonologists or doctors currently in the process of obtaining these specializations. Each physician should include into the Study and observe 10 Patients. Finally, the size of the study group will amount to 3000 patients.

The selection of doctors:

- Paediatricians, general practitioners, internists, allergists and pulmonologists or doctors currently
 in the process of obtaining these specializations who lead the treatment of an appropriate number
 of Patients who meet the Study inclusion criteria under conditions of ambulatory health care
- current license to practice

Recruitment to participate in the Study realisation is done by filling in and submitting the Study Application Form on the basis of which is the qualification is conducted. Due to the limited number of investigators Europharma M. Rachtan Sp. z.o.o. (CRO – Study Organizer) stipulates that the inclusion in the study will be conducted on the first come, first served basis. After the Contract Research Organizer (CRO) has been provided with the original Study Questionnaires, in special cases justified with a research need and where the Investigator is willing to continue the Study (the Investigator shall have a group of Patients meeting the Study inclusion criteria), the Study may be continued by the given Investigator from the moment of the reception of the original questionnaires from the Study Organizer.

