5.2. Inclusion criteria

Study number: EUP/HED/008/2016

VERSION DATE: 21.11.2016

Each study participant must meet the following criteria:

- Patient of either sex, aged 2 to 12
- Diagnosis of a productive (wet) cough of various aetiology

The inclusion into the Study will take place during the 1st visit. Only Patients in which the earlier recommendation to use HEDUSSIN® in the therapy of productive cough of various aetiology was made due to solely medical reasons and independently from this Study, and who did not take the first dose of the syrup at the moment of the inclusion, are eligible. The inclusion of the patient into the group where the given treatment method is used should not result from the study protocol. It should be dependent solely on the current medical practice and remain in accordance with the current medical knowledge.

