10.3. Method of determining the sample size

This is a post-authorization study. The size of the research group (n=500) was determined taking into account some practical limitations associated with the Study realisation and without the use of statistical sample selection tools. This should be taken into account when interpreting the study results.

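### Section 5.1 sets a quota of 10 children per physician without consecutive enrolment or a count of eligible children left out, and lets investigators continue after their outcome data are handed in, with no outcome-independent criterion or cap

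*Protocol*

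**What the plan says.** Protocol section 5.1 gives the plan as "The study is planned to include 500 patients treated in Poland by 50 paediatricians" and doctors of other named specialties, and then: "Each physician should include into the Study and observe 10 Patients". The next sentence gives a different total: "Finally, the size of the study group will amount to 3000 patients". The only list required of the investigator is of children already included.

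The same section has a continuation clause. It opens "After the Contract Research Organizer (CRO) has been provided with the original Study Questionnaires, in special cases justified with a research need", adds that the investigator must be willing and must have further eligible patients, and concludes that "the Study may be continued by the given Investigator". The research need is not defined, no maximum number of further patients is given, and the clause does not say who decides or on what information. Under section 3.3 the questionnaires carry the efficacy data. Under section 3.1.2 the study is open-label and non-randomised.

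Section 5.2 has two safeguards. The recommendation to use the product must have been made for medical reasons and independently of the study: "The inclusion of the patient into the group where the given treatment method is used should not result from the study protocol". Inclusion takes place at visit 1, and the child must not yet have had the first dose. Section 8.2 numbers patients in the order in which they were included. Section 10.3 says that the size was set on practical grounds, "without the use of statistical sample selection tools".

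**The concern.** The section 5.2 safeguards govern the decision to prescribe and the time of entry. They do not say which of the children already prescribed the product are then observed. Section 3.1 treats inclusion as separate from the treatment decision, and no rule governs that second step. Numbering children in order of inclusion is not the same as including eligible children in order of attendance. A physician who sees more than 10 eligible children in the three months can therefore fill the quota with any 10 of them and still comply with the protocol.

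The continuation clause is a second point at which the composition of the sample can change, and it comes after outcomes are on paper with the organiser. Under sections 12.5, 13.3 and 13.4 the organiser also manages the data, writes the report and contracts the investigators.

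There is no comparator, so the change from visit 1 to visit 2 and the days to recovery carry the efficacy conclusion. Any selection on prognosis or results passes straight into them. Because children left out are not counted, and sections 12.1 and 12.3 provide for no audits and no source data verification, nobody could later check whether selection took place. Sections 10.5 and 10.6 do not list it among the modifying factors or limitations. Sections 1.3 and 3.3 say that the results will be used in marketing and training, so it matters that they describe routine use.

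**Working it through.** **The plan's own figure.** 50 physicians × 10 patients = 500, which reproduces the planned size. The 3000 in the same section does not follow: it would need 3000/50 = 60 patients per physician, or 3000/10 = 300 physicians. The possible extent of continuation is therefore unclear.

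The protocol gives no outcome SD, no number of eligible children per physician and no between-physician variation. Every input below other than 50, 10 and 500 is an assumption, with the outcome SD set to 1.

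**Choice of children at enrolment.** Suppose a physician includes the fraction f of eligible children with the best expected prognosis, and that expectation correlates r with outcome. The sample mean then shifts by r × i, where i = φ(z)/f and z is the normal cut-off for the upper fraction f.

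- f = 10/30: i = 0.364/0.333 = 1.09. For r = 0.1 to 0.2 the shift is 0.11 to 0.22 SD.
- f = 1/2: i = 0.399/0.5 = 0.80, shift 0.08 to 0.16 SD.
- f = 1/5: i = 0.280/0.2 = 1.40, shift 0.14 to 0.28 SD.

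A simulation that takes the best 10 of M eligible children (20,000 replicates) gives these shifts in SD:

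| M | r = 0 | r = 0.1 | r = 0.3 | r = 0.5 |
|---|---|---|---|---|
| 10 | 0 | 0 | 0 | 0 |
| 15 | 0 | 0.05 | 0.16 | 0.26 |
| 20 | 0 | 0.08 | 0.23 | 0.38 |
| 30 | 0 | 0.11 | 0.32 | 0.53 |

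The shift is nil if a physician sees only 10 eligible children, and nil under consecutive enrolment (r = 0).

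**Scale against sampling error.** With independent patients the standard error of a mean at n = 500 is 1/√500 = 0.0447 SD, so 0.11 to 0.22 SD is 2.4 to 4.9 standard errors. With an assumed ICC of 0.05 and 10 children per physician the design effect is 1 + 9 × 0.05 = 1.45. The multiples then fall by √1.45 = 1.20, to about 2.0 to 4.1. Clustering changes the multiples but not the shift.

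**Continuation.** Suppose the k best-scoring of 50 physicians, ranked on the mean of their first 10 patients, each add m patients. The pooled mean shifts by approximately

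km/(500 + km) × i × ICC/√(ICC + (1 − ICC)/10).

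For k = 10 of 50, f = 1/5 and i = 1.40. With m = 10 the first factor is 100/600:

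- ICC 0: 0.
- ICC 0.05: (1/6) × 1.40 × 0.05/√0.145 = 0.03 SD.
- ICC 0.10: (1/6) × 1.40 × 0.10/√0.190 = 0.05 SD.
- ICC 0.20: (1/6) × 1.40 × 0.20/√0.280 = 0.09 SD.

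A simulation (4,000 replicates) gives 0.00, 0.03, 0.05 and 0.09 SD. If each of the 10 adds 50 patients, the simulated shifts are 0.00, 0.09, 0.16 and 0.26 SD. A continuation rule that ignores outcome gives 0 throughout.

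**The case against.** A reader might infer that physicians pick children who respond well. The protocol does not support this. Section 5.2 puts inclusion at visit 1, before the first dose, so a physician who follows the protocol cannot know the response. Only expected prognosis is available at that point. Nor does any section grant a free choice of children: the latitude follows from the absence of a rule.

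A reader might also infer that the organiser lets successful investigators go on because of their results. Section 5.1 does not say so. Its stated conditions are special cases, a research need, a willing investigator and further eligible patients, and it does not name the person who decides. Handing in original questionnaires before more patients are entered could be a paperwork rule. Physicians are first admitted in order of application, which is independent of outcome.

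The sizes rest on assumed inputs, and so does their direction: physicians might favour sicker children, families likely to return, or whoever is at hand. If each sees about 10 eligible children, enrolment selection disappears. Multiples of the standard error also make any fixed bias look large at n = 500. Section 10.3 already tells readers to bear in mind how the group size was set.

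These objections remove any claim that selection is planned or has occurred. They leave the gap in place. The section 10.3 caution concerns how the group size was set and does not mention which children are taken. Enrolment and continuation rules belong in the protocol, and an analysis plan could not repair their absence afterwards.

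**Conclusion.** The point holds in a limited form. Section 5.1 has no consecutive-enrolment rule, no count of eligible children left out, and no outcome-independent criterion or cap for continuation. Selection towards favourable results therefore cannot be excluded or checked. It can arise in two ways only: on expected prognosis at enrolment, or on observed results through continuation, and the second biases the mean only where physicians truly differ.

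The illustrative size is 0.11 to 0.22 SD for 10 of 30 eligible children at a correlation of 0.1 to 0.2, falling to 0 if only 10 are seen. For 10 of 50 physicians each adding 10 patients it is 0 to 0.09 SD over an ICC of 0 to 0.20. These figures show what modest selection could do and are not estimates for this study. The weakness is in the sampling method and is cheap to improve; apart from the 500 and 3000 totals, it is not a contradiction in the protocol.

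**What to change.** In section 5.1:

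- Require each physician to include the first 10 consecutive eligible children already prescribed the product after site start.
- Keep an anonymous tally at each site of eligible children not included, with age, sex and reason.
- Allow continuation only to make up a shortfall in total accrual, decided on enrolment counts without reference to outcomes, with a fixed cap per investigator.
- Reconcile the 500 and 3000 totals.

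This changes no treatment, visit or procedure and fits a non-interventional design. The cost is a few sentences in the protocol, one tally sheet per site and slightly less flexibility in recruitment.

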DESIGN OF THE STUDY:	The staff that will take part in the study consists of paediatricians, general practitioners, internists, allergists, pulmonologists or doctors currently in the process of obtaining these specializations who lead the treatment of patients (in the form of outpatient healthcare) suffering from productive cough of various aetiologies in which, due to clinical indications, the HEDUSSIN® medicinal product has been introduced. Data on the efficacy of the treatment with the HEDUSSIN® medicinal product will be gathered in the Study Questionnaires (SQ) during two subsequent routine visits: first (1), where the Patient will be included in the Study, and second (2) approximately 7-10 days after the first one. The visits will be scheduled in accordance with the needs resulting from the Patient's clinical state. The inclusion of the Patient into the group where the given treatment method is used should not result from the Study Protocol. It should be dependent solely on the current medical practice and remain in accordance with the current medical knowledge. The medical history collection period, conducted by 50 investigators, is scheduled for 3 months.	
STUDY POPULATION	Patients (N=500) aged 2-12 of both sexes, diagnosed with productive (wet) cough of various aetiologies.	
MEDICINAL PRODUCT TO BE USED IN THE STUDY	In 100ml of the syrup, HEDUSSIN ® contains 825g of dry extract of ivy leaves. It is a medicine in the form of a brown, opalescent liquid of sweet flavour, possibly with a light sediment. HEDUSSIN ® is recommended productive (wet) cough of various aetiologies as an expectorant.	
ENDPOINTS:	Endpoints and methods of their assessment:	
	The gathering of information on the therapeutic effects of the treatment with the HEDUSSIN® medicinal product based on the evaluation of the severity of the symptoms associated with the respiratory system, the Patient's overall wellbeing and the duration of the infection. All adverse effects caused by the drug must be reported to Phytopharm Klęka S.A. and to the URPL. Additionally, they can be reported to the Study Organizer via the website:	
AT 4 TIQT: 2	www.dzialanianiepozadane.com	

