STATISTICAL METHODS:	The sample size of 500 Patients was based on the feasibility study. The analysis of the data obtained in the Study will be descriptive: the compiled data will consist of summarizing statistics such as quantities, average values, standard deviations, medians, minimal and maximal values of the observed frequencies/proportions. The effectiveness analysis will be conducted on the basis of the population of Patients who will partake in all of the visits described in the Study Protocol.	

Table of contents

Study number: EUP/HED/008/2016 VERSION DATE: 21.11.2016

1. INT	RODUCTION	6
1.1.	Basic information on the subject affliction of this Study	6
1.2.	Information on the study drug	7
1.3.	The clinical reason for conducting this Observational Study	8
2. TH	E AIM OF THE STUDY	9
2.1.	The main aim of the Study	9
2.2.	The additional aim of the Study	9
3. STU	JDY DESIGN	10
3.1.	Basic information	10
3.1.	1. Characteristics of the study population	10
3.1.2	2. Study design	10
3.2.	Endpoints	10
3.3.	Substantiation of the study construction	10
3.4.	Duration of the Study	11
4. CO	MPLIANCE WITH TERMS OF GOOD CLINICAL PRACTICE, ETHICAL ISSUES.	11
5. STU	JDY POPULATION	11
5.1.	Records of the Study participants	11
5.2.	Inclusion criteria	12
5.3.	Exclusion criteria	12
5.4.	Procedures for treatment discontinuation or if the patient withdraws from the study	12
6. ME	THODOLOGY	12
6.1.	Schedule of the Study	12
6.2.	Assessments in a specialist and primary care clinics under the study	13
6.2.	1. Initial visit (Visit 1) - (day 0)	13
6.2.2		•
	the clinical needs of the Patient	
	SESSMENTS PERFORMED IN THE STUDY	
7.1.	Endpoints and the methods of their evaluation	
7.1. ⁻		
	JDY DRUG	
8.1.	Administration of the drug	
8.2.	Patient identification	
8.3.	Drug delivery	
8.4. 9. REI	Concomitant medication PORTING RELATED ADVERSE EFFECTS	
	TATISTICAL CONSIDERATIONS	
10. 5		
IU.I.	F QUEIL GIQSSIIIGAUUT ATU UEIITIUUT	10

DOCUMENT

STATUS: CONFIDENTIAL

10.2	2.	Analyses, populations, definitions	16
10.3	3.	Method of determining the sample size	17
10.4	1.	Statistical analysis	17
1	0.4.1	. Demographic data and other basic characteristics	17
1	0.4.2	2. Distribution of patients and cases of exclusion from the study	17
1	0.4.3	3. Adverse effects analysis	17
10.5	5.	Factors which may affect the statistical analysis and modify the results of the Study	18
10.6	6.	Factors limiting the Study	18
11.	M	ONITORING PROCEDURES	18
12.	MA	ANAGEMENT OF THE STUDY	18

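### Section 5.1 gives the study size as both 500 and 3000; only 500 follows from 50 physicians with 10 patients each, and the 1/1000 safety claim in section 10.6 does not fit 500

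*Protocol*

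**What the plan says.** Section 5.1 gives the enrolment plan in three consecutive sentences. The first sets the total and the number of physicians: "The study is planned to include 500 patients treated in Poland by 50 paediatricians" (the list of specialties continues). The second sets the quota: "Each physician should include into the Study and observe 10 Patients". The third closes the paragraph: "Finally, the size of the study group will amount to 3000 patients".

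The size is stated in four other places, each time as 500:
- Protocol summary, study population: "Patients (N=500) aged 2-12 of both sexes".
- Protocol summary, statistical methods: "The sample size of 500 Patients was based on the feasibility study".
- Section 3.3: 500 patients within a three-month study.
- Section 10.3: "The size of the research group (n=500) was determined taking into account some practical limitations". The same sentence adds that no statistical sample-size tool was used.

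The design row of the summary repeats the number of physicians: "The medical history collection period, conducted by 50 investigators, is scheduled for 3 months".

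Section 10.6 does not give a study size but depends on one. It says the safety analysis will allow the frequency of adverse effects above 1/1000 to be assessed, covering the very common, common and uncommon classes, and that rare and very rare effects are out of reach.

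**The concern.** A protocol should give one enrolment total. Here one paragraph gives two, six-fold apart, and the second does not follow from the two numbers just before it. Section 10.3 says the size was not derived statistically, so there is no significance level, power or effect size from which a reader could work out which figure was meant. The stated number is all there is.

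The choice also affects what the study can claim about safety. The threshold in section 10.6 is plausible for about 3000 patients but not for 500. If 5.1 is corrected and 10.6 is left alone, the protocol will still promise more than its sample can deliver.

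**Working it through.** **Inputs.** Physicians: 50 (section 5.1; summary, design). Patients per physician: 10 (section 5.1). Stated totals: 500 (section 5.1, summary twice, sections 3.3 and 10.3) and 3000 (section 5.1 only). Safety threshold: 1/1000 (section 10.6).

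**Step 1: reproduce the stated size.** Physicians x patients per physician = 50 x 10 = 500. This gives the first figure in 5.1 and every figure elsewhere. It does not give 3000; 3000 / 500 = 6.

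**Step 2: look for a route to 3000.**
- More patients per physician: 3000 / 50 = 60, against a stated 10.
- More physicians: 3000 / 10 = 300, against a stated 50.
- Allowance for dropout, with 500 as the number of completers: 500 / (1 - d) = 3000 gives d = 1 - 500/3000 = 83%. The protocol states no dropout rate. Assumed rates of 10%, 20% and 50% would give 556, 625 and 1000.
- A second cohort, phase or extension target: none is described.

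None of these supports 3000.

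**Step 3: what each size means for section 10.6.** Assume that all n patients contribute safety data, that patients are independent, and that any event is recorded. The chance of at least one case of an effect with true rate p is 1 - (1 - p)^n.

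| | n = 500 | n = 3000 |
|---|---|---|
| Expected cases at p = 1/1000 (n x p) | 0.5 | 3 |
| Chance of at least one case, 1 - 0.999^n | 39.4% | 95.0% |
| Rate seen at least once with 95% probability, 1 - 0.05^(1/n) | 0.00597, about 1/167 | 0.000998, about 1/1000 |

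Section 1.2 defines uncommon as 1/1000 up to 1/100. At the upper end, p = 1/100, 500 patients give 1 - 0.99^500 = 99.3%. So 500 patients suffice to see very common and common effects and the more frequent part of the uncommon class, down to about 1/167, but not the stretch from there to 1/1000. Seeing one case is also a lenient standard, since section 10.6 speaks of assessing a frequency.

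**The case against.** The strongest reply is that 3000 is one stray figure in an otherwise consistent design. Section 10.3, which governs sample size, says 500. The number of physicians, the quota and the three-month duration all fit 500, and the study is single-arm and mainly descriptive. This largely stands. It is why 500 can be named as the evident intention, and why the point should be kept narrow. It does not remove the contradiction, which sits in current protocol text.

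Three stronger readings are tempting, and the documents do not support them.

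- **Recruitment has no fixed end.** A reader might infer that any total from 500 to 3000 would comply. But three months, 50 physicians and 10 patients each bound recruitment, and 3000 would break the physician number or the quota.
- **Continuation steered by outcomes biases the result.** A later paragraph of 5.1 says that "the Study may be continued by the given Investigator from the moment of the reception of the original questionnaires from the Study Organizer". A reader might infer that physicians with favourable returned questionnaires would be kept on, or that continuation explains the 3000. The clause covers only special cases with a research need, a willing investigator and eligible patients. It gives no number, so it cannot supply the missing 3000 - 500 = 2500 patients. Nothing says that returned outcomes are looked at in deciding who continues. It does not rule that out, but a biased result is speculation, and the clause would read the same with 3000 corrected.
- **Planned precision is lost.** Interval widths do scale by sqrt(6) = 2.45 between the two sizes. But the protocol specifies no confidence interval and no power or precision target. The summary lists descriptive statistics, and section 10.4 adds unspecified tests of change.

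One observation points the other way: the 1/1000 statement in 10.6 fits 3000 better than 500. That is no evidence that 3000 was intended, since no stated size agrees with it, but it means that correcting 5.1 alone is not enough.

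**Conclusion.** The point holds in a narrow form. Section 5.1 contradicts itself by a factor of six, and 3000 conflicts with the 50 x 10 design and with every other stated size. Because the enrolment total is a protocol commitment and the correction is almost free, it should be made.

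If 500 is confirmed, the limit in section 10.6 is overstated by about the same factor of six: the rate detectable with 95% probability is about 1/167 rather than 1/1000, and a 1/1000 effect has about a 39% chance of appearing even once. These figures assume complete safety data on all 500 patients; losses would make them worse.

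That 500 is the intended total is an inference from the consistency of the other statements. Whether 3000 is a leftover from another text or a slip cannot be told from the document.

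**What to change.** 1. Have the sponsor confirm that the intended total is 500, and replace 3000 with 500 in the last sentence of the enrolment paragraph in section 5.1.
2. Then restate the safety limit in section 10.6 for 500 patients. For example: with 500 patients an adverse effect with a true rate of about 1/167 or higher would be seen at least once with 95% probability, and the chance for an effect at 1/1000 is about 39%. Remove the suggestion that the whole uncommon class can be assessed.
3. If the sponsor instead says that 3000 was meant, the physician number or the quota, and every statement of 500, would have to change to match.

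Items 1 and 2 cost a few sentences of protocol text, with no extra patients, visits or data. This point requires no change to the continuation clause.
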